#### Parent:

- Required safety screening questionnaire to confirm child's safety in the MRI scanner
- *[If the child is randomized to the parent-present buffering condition],* sit in a separate room while connected via video conference call to research staff in the MRI console room for duration of MRI scan (approx. 1 hour)

Child:

- Required safety screening questionnaire to confirm child's safety in the MRI scanner
- Saliva sampling at 10 time points throughout the testing session to assess levels of stress-sensitive compounds, including cortisol, alpha amylase, and DHEA.
- Children chew on an absorbent sponge for 1-2 minutes to acquire each saliva sample.
- Measure height and weight using a stadiometer.
- Practice in a pretend MRI machine to gain familiarity with the scanning environment and assess comfort in the scanner bore (i.e., rule out claustrophobia)
- Standard non-invasive structural and functional MRI scanning for 1 hour at 3-Tesla (clinical standard) field strength.
- Collection of physiological data during the MRI scan (respiration belt, and pulse oximeter and/or 3 EKG leads).
- Performance of a social evaluative stress test during MRI scanning.  
(1) Five minutes of silent preparation of a speech about oneself, (2) Oral delivery of the speech to two judges in white lab coats, visible by video feed via video conference call, and (3) Performance of challenging, but age-appropriate math problems under timed limited conditions, while observed by the same two judges. To increase the social evaluative component of the stress, youth are told that we will be video recording their speech and will show it to a panel of kids their age who will rate their performance. Although, we do video record, we will not show anyone the child's performance. The social evaluative stress created by this test depends upon both the visible judges and the belief of a recording that is shown to peers. Without one of these aspects, the stress test does not reliably produce a stress response in the studied population. The research goals of this study cannot be met without a reliable and standard social evaluative stress test. This is standard practice of the Trier Social Stress Test. This recording will be used for training and data purposes only.
- Completion of a post-scan survey to assess perceived stress at various points throughout the session.
- Debriefing of participant to reveal deception (no kids evaluating the recording, two judges were also not actually evaluating performance).

5.2 Study Procedures:

**Social Buffering Manipulations:** Will include 3 between-subjects conditions and both sexes. Participants will be randomly assigned to No Social Partner, Stranger/Experimenter, or Parent.

**Stressor Paradigm:** MISTiC paradigm while the child is lying in the MRI scanner; includes two judges (one male, one female). After consent, youth are separated from their parents and taken for completion of questionnaires (approximately 20 minutes). Youth are taken to a private changing room to change into hospital scrubs prior to moving to the MRI scanner. An MRI-safe respiration belt and pulse oximeter and/or EKG electrodes are positioned for autonomic assessment and the child is given ear plugs, a button response box for math task, and an emergency call button. Youth rest and/or watch a video of their choosing during structural MRI sequences (6-10 minutes), then lie quietly with eyes open for a 5-minute scan with no video or audio material. They are then given an overview of the speech task and are told that they have 5 minutes to prepare. MRI data are collected during the 5 minutes of speech prep, following which the child is introduced to two judges who are visible on the child's video screen and who ask the child to perform their 5 min speech. No MRI data are collected during speech performance. At the end of the speech, the judges give the child instructions for the math performance section, and the child performs multiple-choice math problems that appear on the video screen using the button response box. MRI data are collected during math performance and judges remain visible on the screen during math performance. Following the judged math, judges leave the screen and youth rest or watch a video for 10 minutes during diffusion scanning. Finally, children perform another set of multiple-choice math problems with no judges present (photo of the same judges turned away) while MRI data are collected. Children are removed from the scanner and immediately complete a stress questionnaire and a debriefing session. Saliva samples are collected every 10-20 minutes throughout the session, including between scan segments, to assess dynamic changes in stress-related hormones. In the scanner, this involves handing a long collection sponge to the child which hangs out of the mouth to avoid any possibility of choking since the child is lying supine. We have used this method successfully in a previous study collecting saliva in the scanner environment. Following debriefing, the child will change back into their own clothing and return to the lobby to complete additional questionnaires for 30 min while being sampled for cortisol every 10 min.

Note: As part of the stress challenge, we tell youth that their speech and judged math performance will be video recorded and rated by a group of kids their age. However, we will not actually share their performance with anyone.

**Pubertal Development:** We will create a summary pubertal development index from several measures. All youth will complete the Morris and Udry (1980) pubertal development questionnaire, which allows placement in the gold-standard Tanner stages for hair, testicles, and breast development ([Tanner, 1962](#)). In all studies target participants will complete the Morris and Udry questionnaire within 2 weeks before the experimental sessions described below. We will also analyze salivary DHEA to augment our measures of puberty ([Shirtcliff, Dahl, & Pollak, 2009](#)).

**Questionnaires.**

**Forms will be completed either on paper or online via Redcap.**

**Demographic Questionnaire:** Parents will complete information on pre-tax family income, education level of parent(s), composition of the household, and medications that the child regularly takes.

**Daily Diary:** The parent and the youth both will report the following for the child that day: the time of wake up, medication usage, illness/fever, physical activity, and caffeine consumption.

**Relationship Quality:** Participants will complete the Network of Relationships Inventory - Behavioral Systems Version (NRI-BSV, Furman & Buhrmester, 2009) for the parent who accompanies them and their close friend. This questionnaire is based on an integration of attachment and Sullivanian theory and assesses three systems that are expected to be key in close relationships: attachment, caregiving and affiliation. The scales are: companionship, seek safe haven, seek secure base, provide safe haven, provide secure base, conflict, antagonism and criticism. We will also add 3 scales from the NRI-Relationship Qualities Version: Emotional Support, Approval and Satisfaction. Each scale consists of 3 items scored on a 5-point Likert scale. Psychometric qualities are high. Condition differences in quality of relationships will be examined and included as covariates if groups differ significantly. Otherwise, in follow-up analyses we will examine whether social buffering effects are stronger in relationships the child views as more supportive.

**Four additional NRI scales (Seek Safe Haven, Seek Secure Base, Provide Safe Haven, Provide Secure Base) will be collected to better measure relationship quality. Completed participants will be contacted to complete these additional 12 questions and will be compensated for their time.**

**MacArthur Health and Behavior Questionnaire (HBQ) for 9-18 Year-Olds (Parent and Child, 2.1):** This questionnaire was developed by Marilyn Essex based on the original HBQ for 4-8 year olds. We have used it many

times. The scales we proposed to use here have high reliabilities (Cronbach alpha's > .8). We will use the peer scales (acceptance/rejection, bullied, relational victimization, asocial, behavioral inhibition) and broad-band symptoms scales (Internalizing, Externalizing). These measures will be examined for balance across groups and if differences by condition, pubertal stage, or sex are found, will be entered as covariates.

**Self-Report of Stress:** As a manipulation check, participants will rate their arousal and emotional state at various points during Visit 2.

**Version 3.0 addition:** Added Child-self-report RSQ for Peer, Family, & Academic Stress, and PALS Student report of adaptation to challenge in environment.

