## PROTOCOL TITLE: An MRI Study of Stress and Social Support

VERSION DATE: v.5.5 2022.09.20

		section 17.2 and removed references to involvement of a friend in section 13.1	
9 (v5.1)	Jan 15, 2021	Added video recording of sessions. Consent form updated to clarify recording.	Yes
10 (v5.2)	May 25, 2021	Added new NRI questionnaire version and contacting past participants to complete this addition, with payment of \$10 via online gift card or ClinCard.	
11 (v5.3)	Oct 27, 2021	Added recruitment method of contacting organizations through email.	No
12 (v5.4)	Aug 18, 2022	Added recruitment methods of mailing paper flyers and contacting people through organization listserv.	No
13 (v5.5)	Sep 20, 2022	Increased child payment to \$100 total and parent payment to \$50 total.	Yes

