#### Children/adolescents:

- Questionnaire about general health, behavior, and development (MacArthur Health Behavior Questionnaire; HBQ)
- Questionnaire about their relationships with their parents and their best friend (Network of Relationships Questionnaire)
- Pubertal development questionnaire (Morris and Udry, 1980)
- Safety screening questionnaire to confirm safety in the MRI scanner

**Visit 2:** Parent and child will come to the Center for Magnetic Resonance Research for a session lasting approximately 2 hours. Following a session overview and consent/assent procedures, participants will be asked to complete the following measures:

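### Early completers rate four NRI scales after the randomised visit, and nothing keeps those late ratings out of the covariate and moderator rules

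*Combined protocol and SAP*

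**What the plan says.** **Timing.** In Section 5.1 (Study Overview), the child's NRI is among the Visit 1 measures. The stress test under the assigned condition, and then the debriefing, take place at Visit 2. Revision 10 (v5.2, May 25, 2021) records a change: "Added new NRI questionnaire version and contacting past participants to complete this addition".

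Section 5.2 (Questionnaires, Relationship Quality) gives the content and purpose: "Four additional NRI scales (Seek Safe Haven, Seek Secure Base, Provide Safe Haven, Provide Secure Base) will be collected to better measure relationship quality". It continues: "Completed participants will be contacted to complete these additional 12 questions and will be compensated for their time".

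**Use.** The preceding paragraph of Section 5.2 sets two roles for relationship quality. The first is as a covariate: "Condition differences in quality of relationships will be examined and included as covariates if groups differ significantly". The second applies otherwise: "in follow-up analyses we will examine whether social buffering effects are stronger in relationships the child views as more supportive". Section 15.1 adds a general rule that variables associated with both the independent variables (condition, sex, pubertal stage) and the outcomes are controlled for in the primary analyses.

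**Not stated.** The documents give no collection date relative to Visit 2, no restriction of either role to Visit 1 ratings, and no sensitivity analysis without the late ratings. They do not say how many children were re-contacted or after what delay. They also do not say whether the 12 questions concern the parent, the friend or both. Section 5.2 lists the same four scales as already belonging to the NRI-BSV and then calls them additional.

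**The concern.** A rating made before randomised exposure can differ between conditions only by chance. A rating made afterwards can differ because of the condition. A rule that tests for a difference and then adjusts cannot tell these apart. If the parent condition raises a child's later rating of turning to the parent for security, adjusting for that rating removes part of the effect under study.

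The moderator analysis has a related weakness. A child who felt helped during the test may afterwards describe the relationship as more supportive. An apparent finding that buffering is stronger in supportive relationships could then reflect the order of measurement. Two of the four scales, Seek Safe Haven and Seek Secure Base, lie close to what the parent condition supplies.

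**Working it through.** **1. The stated count.** The plan says "Each scale consists of 3 items scored on a 5-point Likert scale". Four scales x 3 items = 12, which agrees with the number of additional questions.

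**2. Order of events.** Children tested under the NRI plan in Section 5.1 go: Visit 1 NRI, assigned condition and stressor, debriefing. Re-contacted children go: Visit 1 (other NRI scales), assigned condition and stressor, debriefing, four added scales. On those four scales the data set mixes ratings from before and after exposure.

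**3. Inputs for size.** From the documents: 200 children, three conditions. Assumed, because the documents give no figure: true parent effect b = -0.50 SD; rating-outcome correlation g = -0.30; share of late raters p; shift d, in SD, that the parent condition causes in a late rating.

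**4. Effect if the rating were always adjusted for.** The observed rating in the parent condition moves by p x d on average, so the adjusted effect is approximately b - g x p x d.

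- Half late, 0.5 SD: -0.50 + 0.30 x 0.25 = -0.425
- Half late, 0.8 SD: -0.50 + 0.30 x 0.40 = -0.38
- Quarter late, 0.3 SD: -0.50 + 0.30 x 0.075 = -0.4775

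Simulation (arms of 67/67/66) gives about -0.43, -0.39 and -0.48, in agreement.

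**5. Effect under the plan's conditional rule.** The plan adjusts only when the conditions differ significantly. Each simulated trial tests the rating across the three conditions at p < .05. It keeps the adjusted estimate if the test is significant and the unadjusted one otherwise.

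| Single scale | Test significant | Always adjusted | Average under the rule | Loss |
|---|---|---|---|---|
| None late | about 5% | -0.50 | -0.50 | none |
| Quarter late, 0.3 SD | 7% | -0.48 | -0.495 | 0.005/0.50 = 1% |
| Half late, 0.5 SD | about 30% | -0.43 | -0.47 | 0.03/0.50 = 6% |
| Half late, 0.8 SD | about 62% | -0.39 | -0.41 | 0.09/0.50 = 18% |

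The fourth column is not a simple weighted mean of adjusted and unadjusted effects, because the test tends to be significant in the trials where the ratings differ most.

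**6. Dilution.** Section 5.2 names eight NRI-BSV scales and three more, 11 in all, so 11 - 4 = 7 are unaffected. Suppose all 11 are averaged in one direction, with an assumed inter-scale correlation of 0.5. The average effect under the rule is then about -0.49 for half late with 0.5 SD, and between -0.48 and -0.47 for half late with 0.8 SD.

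**7. Moderator role.** Assume no true moderation, and let late ratings in the parent condition carry over 0.3 SD per SD of the child's own response. A significant result in the direction of stronger buffering then appears in about 8% to 11% of trials with half late. The lower figure sets the parent condition against no partner alone, the higher against both other conditions together. With a quarter late it is about 6%, against about 3% with no carry-over.

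**The case against.** **Use of the four scales is inferred.** The covariate and moderator sentences close the paragraph on the main NRI; the added scales come in a later paragraph. No sentence says that they enter the rules, singly or combined. The moderator sentence could also be served by the separate Emotional Support scale. This stands as a limit: the four scales are collected to measure the construct that the rules use, so their entry is a fair reading, but it is not stated.

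**Which relationship.** The NRI covers the accompanying parent and a close friend. No current condition involves a friend, so the mechanism does not apply directly to friend ratings. It would be too strong to describe all 12 items as parent ratings or to say that the plan calls them a baseline.

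**The drivers may be small.** In the parent condition, the parent sits in a separate room on a video call for about an hour. Nothing in the documents suggests that this moves a relationship rating by 0.5 or 0.8 SD. Half late is also only an assumption: re-contact was added in May 2021, and recruitment methods were still being added in October 2021 and August 2022. This limits the size but does not repair the rule.

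**A tempting stronger reading.** From the always-adjusted figures for one scale, a reader might infer that 15% or 23% of the parent effect is lost. Those figures assume that adjustment always happens, whereas Section 5.2 makes it conditional.

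**Conclusion.** The timing is clear from the text: four NRI scales are collected after exposure in re-contacted children, and the plan does not keep those values out of rules that need a pre-exposure rating. A significant condition difference in them should not prompt adjustment, and a moderator result that relies on them would be open to reverse order.

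The size is uncertain and may be small. Across the assumed cases for a single scale, the average loss under the conditional rule runs from about 1% to 18% of an effect of -0.50 SD. Averaging with the other seven scales brings the half-late cases to roughly 2% to 6%. If exposure does not change ratings, the adjustment bias is nil.

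The documents do not support the inference that the NRI as a whole is compromised. Only four scales are affected, and only in children who completed before the scales were added. The point merits a correction because the remedy is cheap, not because a large bias has been shown.

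**What to change.** In Sections 5.2 and 15.1:

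- Record the date of each NRI scale relative to Visit 2.
- Allow only ratings completed before Visit 2 as covariates or moderators, and state that a condition difference in later ratings does not trigger adjustment.
- Report late ratings of the four scales descriptively or in a sensitivity analysis.
- Say whether the 12 items concern the parent, the friend or both, how the NRI scales are combined, and whether the four scales were already part of the NRI-BSV as first administered.

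The cost is a date flag and a few sentences. The four scales will have fewer usable values among early participants, and that gap will follow calendar period. The other NRI scales from Visit 1 are unaffected.

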### **Physiological Measures.**

**Stress Hormones:** We will assay saliva samples for stress sensitive hormones: cortisol and alpha-amylase. Saliva will be collected using SalivaBio Oral Swabs (SOS) or passive drool and stored frozen at -20°C until shipped for assay. All testing will be conducted in the late afternoon to control for circadian rhythm. Medications will be recorded from parent report and classes of drug codes will be used to group meds by presumed mechanisms of action and will be entered as covariates (Granger et al., 2009). Systemic glucocorticoid medications are an exclusion criterion. For each analyte, we will calculate area under the curve from intercept (AUCi) to provide a single measure for the main analysis.

**Pubertal Hormones - DHEA, Testosterone, Estradiol:** Sufficient saliva will be obtained at sampling to assay for these additional pubertal hormones. These assays will be performed if we obtain a sex by condition by pubertal development (3-way) interaction on key outcome measures. If so, these measures may provide insight into the mechanism of these interactions ([Butler et al., 1989](#); [Mehta, Mor, Yap, & Prasad, 2015](#)).

**Physiological Recording:** Participants will wear standard Siemens physiological recording equipment for the MRI environment (respiration belt, and pulse oximeter or EKG leads). Samples will be collected throughout the entire MRI scan. Response measures will be computed by regressing the stress condition values on comparison condition values and saving the residual as the response measure.

All questionnaires and surveys are included in the ETHOS portal. Contact information and child age will be obtained from an existing registry of families who have expressed interest in child development research (specifically, parent name(s), address, phone number, email address, child

**PROTOCOL TITLE:** An MRI Study of Stress and Social Support

**VERSION DATE:** v.5.5 2022.09.20

name, child sex, and child birthdate). All other data will be acquired directly from the participants, and information obtained from the participant registry will be verified verbally with the parent.

**5.3 Study Duration:** Participants will attend two sessions. Each session will last approximately 2 hours.

- All participants will be enrolled and assessed within a 30-month period.
- Primary data analysis endpoints will be available within 1 year of the end of data collection (i.e., 42 months from initial enrollment).

**5.4 Individually Identifiable Health Information:** This study will collect health information directly from participants. A HIPCO survey has been uploaded in the ETHOS portal.

**5.5 Use of radiation:** N/A

**5.6 Use of Center for Magnetic Resonance Research:** All MRI scanning will occur on a 3-Tesla MRI scanner located at the CMRR. Scans will be conducted by the PI or her study team. No PHI data will be entered into any CMRR computer or equipment; scans will be collected in de-identified form. The CMRR will not have access to any PHI from any participant in this study. Therefore, HIPAA authorization is not applicable in this case.

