## **ABBREVIATIONS/DEFINITIONS**

- fMRI: Functional Magnetic Resonance Imaging
- MISTiC: Minnesota Imaging Stress Test in Children
- TSST: Trier Social Stress Test
- CORT, AUCi: salivary cortisol, area under the curve from intercept
- DHEA: dehydroepiandrosterone
- EKG: Electrocardiogram
- vmPFC: ventromedial prefrontal cortex
- ICD: Institute of Child Development

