### **3.0 Study Endpoints/Events/Outcomes**

- 3.1 Primary Endpoint/Event/Outcome:  
Neural activity in vmPFC, insula, amygdala, and hypothalamus; salivary cortisol, heart rate, and respiration
- 3.2 Secondary Endpoint(s)/Event(s)/Outcome(s):  
Exploration of possible sex differences in different conditions later in puberty but not earlier in puberty.

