## 15.0 Statistical Considerations

*15.1 Data Analysis Plan:*

Preliminary Analyses to Determine Covariates Needed for Primary Analyses. The purpose of collecting data on potential covariates is to identify variables that are correlated with both the independent variable (social buffering condition, sex, pubertal stage) and the primary outcome measures. Those covariates that are associated with the independent and outcome variables will be controlled for in the primary analyses. Those that are not will be used to describe the sample, but will not need to be included in the analyses to obtain unbiased estimates. For each potential covariate, we will conduct correlations or t-tests with pubertal stage, and t-tests, ANOVAs, or chi-square tests (as appropriate) with sex and condition. If data do not confirm to modeling assumptions, we will use nonparametric analogs instead.

Preliminary Analyses of Imaging Data to Yield Primary Outcome Measures: fMRI data will be analyzed in FSL software (version 5.0.10) to generate voxel-wise contrast maps. Mean signal values will be extracted from these maps in a priori regions of interest for every participant using the methods described below. These preliminary analyses are used to generate the fMRI outcome variables of interest. The values of these outcome variables for each participant will be used in the general statistical analyses described in the next section. In total, these preliminary analyses will yield 6 primary task-related outcome variables, and 6 primary connectivity-related outcome variables.

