### 15.3 Statistical Analysis of MRI and non-MRI Outcome Variables:

The following is a list of the analyses that we will perform on the outcome measures. They are classified as to whether they are the primary or mediational analyses. All statistical analyses will be performed in R.

The primary analyses will consist of a series of multiple regression models. For each dependent variable, variation in neural activity, cortisol response, and heart rate response, we will begin by testing the three-way interaction between social buffering condition, sex, and pubertal stage for all outcomes. If the three-way interaction is not significant, we will then examine all two-way interactions. If the two-way interactions are not significant, we will then examine main effects only models. If the three-way interaction is significant, we will not examine any other model. If condition is significant as an interaction or as a main effect, we will examine all pairwise comparisons using Tukey's Honestly Significant Difference test.

Multiplicity of testing. We will correct for multiple comparisons using the Benjamini-Hochberg (BH) correction. The BH method works by controlling the false discovery rate, and relative to the Bonferroni's correction is more powerful, while still adequately protecting against Type I error (Williams, Jones, & Tukey, 1999).

Mediational Analysis. When changes in activity of brain regions differ by condition or condition by pubertal status and we also see condition or condition by pubertal status differences for cortisol, or heart rate, then we will examine whether brain activity differences mediate the neuroendocrine or autonomic differences. This will be examined using path analysis, while controlling for covariates identified in the preliminary

covariate analysis, and will be estimated using the lavaan package in R (Rosseel, 2012).

The significance of all indirect effects will be assessed using bias-corrected 95% confidence intervals (Efron & Tibshirani, 1986), where confidence intervals that are non-overlapping with zero will be considered significant.

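### Cortisol AUCi depends heavily on its starting sample and adjustment for that sample is not prespecified, so precision may be lost in the randomised contrasts

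*Combined protocol and SAP*

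**What the plan says.** Section 3.1 lists the primary outcomes as "Neural activity in vmPFC, insula, amygdala, and hypothalamus; salivary cortisol, heart rate, and respiration". The abbreviations list gives "CORT, AUCi: salivary cortisol, area under the curve from intercept", and section 5.2 (Stress Hormones) reduces each analyte to that one number: "we will calculate area under the curve from intercept (AUCi) to provide a single measure for the main analysis".

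The samples behind it are described in section 5.1 (Visit 2, child procedures), "Saliva sampling at 10 time points throughout the testing session", and in section 5.2 (Stressor Paradigm), "Saliva samples are collected every 10-20 minutes throughout the session, including between scan segments". Nowhere is one of these samples named as the intercept or as the pre-stress baseline, and no averaging of early samples is mentioned.

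For the model, section 15.3 says: "we will begin by testing the three-way interaction between social buffering condition, sex, and pubertal stage for all outcomes". Covariates come from the preliminary screen in section 15.1: "Those covariates that are associated with the independent and outcome variables will be controlled for in the primary analyses". The independent variables in that screen are condition, sex and pubertal stage. The hormone paragraph names medication classes as covariates and nothing else. The power calculation in section 15.2 allows for 12 covariates without listing them.

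Heart rate and respiration are handled differently. Under Physiological Recording in section 5.2, the stress-period value is regressed on the comparison-period value and the residual is the response, so the reference level is adjusted for.

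**The concern.** AUCi takes the total area under the cortisol curve and subtracts the intercept value multiplied by the length of the window. A disturbance in that one sample therefore counts many times more than the same disturbance in any other. The protocol recognises two sources of disturbance. Section 7.1 notes that out-of-range assay values often reflect contamination of the sample, and section 13.0 provides a mock scan to lessen anticipatory stress about scanning.

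A regression adjustment would remove the part of this variation that does not carry through to later samples. A plain change score keeps it. If adjustment is left to the screen, a primary outcome may be analysed with less precision than the planned samples allow, chance differences in starting cortisol between arms are left in the condition contrasts, and whether to adjust is decided after the data are seen.

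**Working it through.** **1. The plan's own figure.** Section 15.2 gives a minimum detectable f² of 0.056 (n = 200) and 0.070 (n = 160) for the three-way term, at alpha .05 and power .80. That term has 2 df. The full model has 12 covariate df + 4 main-effect df + 5 two-way df + 2 three-way df = 23, so the error df are 200 − 23 − 1 = 176, or 136 for n = 160. The noncentral F test with λ = f²(u + v + 1) gives 0.0548 and 0.0709, so the figures reproduce. The calculation contains no term for AUCi variance or baseline correlation, so it neither covers nor contradicts this point.

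**2. Weight of the intercept sample.** Assume ten equally spaced samples with the first as intercept; neither is stated in the documents. Dividing AUCi by window length gives w′y − y₀, with trapezoid weights w = 1/18 for the first and last samples and 1/9 for the other eight. The first sample's net weight is 1/18 − 1 = −0.94. Each middle sample has weight 0.11.

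**3. Variance with and without adjustment, equal variances.** Let each sample have variance 1 and let every pair correlate r.

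- Unadjusted: V_un = (1 − r)[(17/18)² + 8/81 + 1/324] = 0.9938(1 − r).
- Slope of w′y on y₀: b = 1/18 + (17/18)r.
- Adjusted: V_adj = r + (1 − r)(34/324) − b².
- Identity: V_un = V_adj + (1 − b)², so adjustment gains nothing only when b = 1.

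At r = .6: V_un = 0.3975, b = 0.6222, V_adj = 0.6420 − 0.3872 = 0.2548, and the ratio is 0.3975/0.2548 = 1.56.

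| Common r | V_un / V_adj | 200 unadjusted children are worth (adjusted) | Power of planned model when adjusted model has 80% |
|---|---|---|---|
| .4 | 2.17 | 92 | 46% |
| .6 | 1.56 | 128 | 60% |
| .8 | 1.22 | 164 | 72% |
| .9 | 1.10 | 182 | 76% |

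The third column is 200 divided by the ratio. The fourth takes the adjusted model's detectable f² for the three-way term (0.0551 with 175 error df) and divides it by the ratio. If correlation instead decays with distance (AR(1), adjacent correlation .7, .8, .9, .95), the ratios are 2.40, 1.85, 1.38 and 1.18.

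**4. Unequal variances.** Let all nine later samples have k times the SD of the first. Then b = 1/18 + (17/18)rk, which equals 1 when rk = 1.

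- k = 1.25: ratios 1.52, 1.14, 1.00 and 1.10 at r = .4, .6, .8 and .9.
- k = 1.5: ratios 1.23, 1.02, 1.10 and 1.54 at the same r.

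The gain therefore runs from nil to large. The ratio cannot fall below 1, because V_un − V_adj is a square.

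**5. Bias or precision.** If the intercept sample precedes any effect of condition, then at a given pubertal stage its expected value is the same in all three arms, because condition is randomised (sections 4.1 and 5.1). Subtracting it removes the same expected amount from each arm, so the difference cancels from every condition contrast and from condition by puberty. It does not cancel from the puberty or sex main effects, which compare groups that were not randomised.

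**The case against.** The strongest reply is that nothing in the plan excludes starting cortisol. The screen tests candidates against sex and pubertal stage as well as condition. If starting cortisol differs by puberty, it has one of the two required associations, and the subtraction built into AUCi will usually supply the other. The 12 covariates in section 15.2 are unnamed and could include it. This stands in part: the screen could admit it. But admission depends on its being treated as a candidate and on an association with an independent variable, whereas the precision gain depends only on its relation to the outcome. Section 15.1 defends dropping other covariates on grounds of unbiasedness, which does not address precision.

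A reader might infer that a puberty difference in starting cortisol biases the puberty-by-condition estimate. The documents do not support that, for the reason in step 5 of the working. What reaches that estimate is noise and chance imbalance.

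A reader might also apply the two-timepoint rule, in which adjustment is worth 2/(1 + r) times the children: 1.54, 1.33 and 1.18 at r = .3, .5 and .7. That is not the ten-sample AUCi result, and it assumes equal variances. With a later SD 1.5 times the starting SD, the same comparison gives 1.15, 1.04 and 1.002. No fixed dividend can be claimed.

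Finally, adjustment is not neutral for every term. Because pubertal stage and sex are not randomised, conditioning on starting cortisol changes what their main effects mean. This objection stands and shapes the fix.

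**Conclusion.** The point holds as one of precision. Cortisol AUCi loads about −0.94 on its intercept sample, and adjustment for that sample is possible under the plan but not prespecified. The condition and condition-by-puberty contrasts remain valid; they may be less precise than they need be and are exposed to chance baseline imbalance.

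The size is conditional, since the documents give no SDs or correlations. Under equal variances and a common correlation of .4 to .9, unadjusted variance is about 2.2 to 1.1 times the adjusted variance. It can come down to equality if later samples vary more than the first. Adjustment never costs more than its one degree of freedom.

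Two assumptions matter: that the intercept is a single early sample, and that it is taken before condition can affect it. The documents settle neither.

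**What to change.** - In section 5.2 (Stress Hormones), state which sample is the AUCi intercept, and define the pre-stress cortisol value as one taken before the child learns of or is connected to the partner.
- In section 15.3, enter that value as a fixed covariate in every cortisol AUCi model, whatever the section 15.1 screen shows.
- Report the pubertal-stage and sex main effects without the baseline covariate as well, and say which question each version answers.

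This is a free improvement. It uses samples already planned, changes no procedure and costs 1 of about 176 error degrees of freedom. It also brings cortisol into line with the adjustment already planned for heart rate and respiration.
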